4.2.2 Exclusion Criteria

Patients who met the inclusion criteria at all time points were required to be included in the study. Therefore, no specific exclusion criteria were set.

4.3 Date Collection

4.3.1 Demographic data and other baseline characteristics

- Birth date
- Sex: Male/ female
- History of smoking and drinking: Yes/No
- Ethnicity: Han/ another ethnicity
- Diagnosis
- Physical Examination: Modified Rankin Scale (mRS), neurological physical examination.

4.3.2 Medical History

- Past medical history: including current medical conditions (high blood pressure, diabetes, etc.), History of cranial and neurological related surgeries, hemorrhagic stroke.

4.3.3 Information of Procedure

• Before Procedure

- Aneurysm Information (Target): aneurysm location (left/right, C2 petrous segment-C7 terminus), aneurysm size (aneurysm maximum diameter, aneurysm neck width, dome to

neck ratio) and morphology (saccular aneurysm, dissecting aneurysm, fusiform aneurysm), ruptured / unruptured / recurrent and the diameter of the parent artery (Base CTA).

- Laboratory Examination(Clinically significant abnormal results only, that means abnormal laboratory test results that were judged by the investigator to be different from the normal standard values and had certain reference value for the diagnosis of clinical diseases).
- Information of Antiplatelet Function Test Result: platelet aggregation test/thromboelastographic (TEG).
- Information of anti-coagulation and anti-platelet medication: drug name, dosage and frequency of administration are needed.

- **Using Information of Device**

- Microcatheter: product name, model, size
- Coil Usage: Yes/No and number
- Balloon: Yes/No and number
- FRED: number, model, lot number FRED:

- **Information of Procedure**

- Puncture position (femoral artery/radial artery, left/right)
Re-sheathing Performance: Whether re-sheathing after release, re-sheathing times, re-sheathing success or not
- Imaging results of immediate post-operation: stent fully cover the aneurysm neck, good wall apposition, parent artery perfusion, retention of contrast media.
- Procedure complication: Complications of arterial puncture including pain, local bleeding, or injury to the artery, or adjacent nerves. Dissection or perforation of the parent artery, Rupture or perforation of the aneurysm, Vasospasm, Stent thrombosis.

4.3.4 Information of follow up

- Imaging Evaluation of a Target Aneurysm: DSA、MRA、CTA can be accepted.
- Treatment-related hospitalization information or adverse event information: Stroke, Death, Adverse Event, Serious Adverse Event.

4.4 Endpoint

4.4.1 Safety Endpoint

(1) Stroke Rate

Definition: The stroke rate refers to the proportion of stroke patients in the total number of patients.

Collection Content: Record the date of stroke, type (ischemic or hemorrhagic), severity (mild, moderate, severe), location and cause, treatments, or other interventions for stroke, and whether the

stroke resulted in the patient's death. Also assess the relationship of the stroke event to the observational device and the patient's concurrent antithrombotic therapy. All stroke events are assessed by the CEC.

(2) All-cause Mortality

Definition: Mortality refers to the proportion of dead patients in the total number of patients.

Collection Content: Record the date of the death event and whether it was neurogenic. Evaluate the relationship of the death event to the observational device. Neurogenic death is defined as a death event directly resulted from a neurologic cause judged by the Clinical Event Committee (CEC).

(3) Lesion-Related Symptoms or Signs Rate

Definition: Lesion-related symptoms or signs rate refers to the proportion of patients with lesion-related symptoms or signs to total patients.

Collection Content: All neurological related symptoms which were not present at baseline or worsened from baseline will be record including headache, hemiplegic paralysis, seizure, aphasia, stroke, bleeding (including intracerebral, subarachnoid hemorrhage, retroperitoneal, others), facial nerve pain, seizures, vision loss, aphasia, hemiplegia, oculomotor nerve palsy, neck pain or stiffness, loss of consciousness, meningeal irritation, pre-retinal hemorrhage, increased intracranial pressure, other aneurysm-related symptoms, or abnormal signs (list specific symptoms or abnormal signs).

(4) Lesion-Related Complication Rate

Definition: Lesion-related complication refers to the proportion of patients with lesion-related complication to total patients.

Collection Content: Record whether the following complications occurred during the procedure. Principal Investigator (PI) shall evaluate the relationship between complications and observational device, other interventional devices, and surgical procedures.

- Complications of arterial puncture: including puncture site pain, puncture site local bleeding, injury to the puncture artery or adjacent nerves,;
- Dissection or perforation of the parent artery,
- Rupture or perforation of the aneurysm,
- Vasospasm;
- Stent thrombosis,
- Other complication

(5) Adverse Event, Serious Adverse Event (AE, SAE)

Definition: Refer to section 10 in this protocol.

Evaluation method: All Adverse Events (AEs) observed or reported will be assessed and recorded, and the causality and severity of AEs will be assessed according to the definitions and causality

assessment in Section 11 of this protocol.

The Principal Investigator (PI) shall assess whether an AE/ SAE meet the definition of surgical complication and safety collection index. If yes, the investigator shall complete corresponding surgical complication or safety evaluation indicator page.

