4.1 Overall Design and Selection Rationale

This is a post-market, retrospective, multi-center, observational clinical study.

The study plans to enroll patients who meet the eligibility criteria and have received at least one implantation of the observational device between May 2023 and May 2027. The retrospective data will be collected on baseline characteristics, information of procedure, and safety and efficacy endpoint to assess the safety and efficacy of FRED in the Chinese population. The efficacy endpoints include technical success rates and re-sheathing performance, the complete occlusion rate, and modified Rankin Scale (mRS) change from baseline. The safety endpoints include the rates of stroke, mortality, lesion-related symptoms or signs rate, lesion-related complication rate, adverse event, serious adverse event.

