4.4.2 Efficacy Endpoint

(1) Imaging Evaluation of a Target Aneurysm (O' Kelly-Marotta, (OKM))

Definition: Based on the evaluation of imaging results, the treatment of aneurysms was classified according to the following criteria. Digital Subtraction Angiography (DSA), Magnetic Resonance Angiography (MRA), or Computed Tomography Angiography (CTA) are acceptable, and it is recommended base CTA. The purpose of imaging follow-up information collection is to observe the effect of on the long-term closure of the aneurysm after treatment. Complete closure of the aneurysm would be associated with increased safety.

- No filling
- Entry remnant (<5%)
- Subtotal filling (5%~95%)
- Total filling (>95%)

The observational device with the blood flow and the aneurysm gradually closes. The evaluation results of different follow-up nodes were counted, and the time interval between the date of surgery and the aneurysm occlusion is collected.

(2) Adequate Occlusion Rate of Target Aneurysm

Definition: Adequate Occlusion is defined as Raymond-Roy Grade I or Grade II on imaging evaluation of the target aneurysm ^[5]. If the Raymond-Roy grade reaches Grade I at any evaluation point, no further imaging information will be collected. Imaging results obtained via Digital Subtraction Angiography (DSA), Magnetic Resonance Angiography (MRA), or Computed Tomography Angiography (CTA) is acceptable. The imaging results will be evaluated following the routine procedures of the clinical research institution. The post-procedure recanalization of the aneurysm is graded according to the following classification. Please refer to **Error! Reference source not found.** for Raymond-Roy Classification Standards.

Table 4-1 Raymond-Roy Classification Standards

Grade	Description
Grade I	Complete occlusion (no contrast filling in the aneurysm sac or neck)
Grade II	Neck remnant (contrast filling in the aneurysm neck but not the sac)
Grade III	Residual sac (contrast filling in the aneurysm sac)

Occlusion Rate of Target Aneurysm refers to the proportion of patients judged to be Grade 1 or Grade 2 in the total number of patients.

(3) Technical Success Rate

Definition: Technical success is defined as successful stent placement and meet following criteria:

- Stent fully cover the aneurysm neck
- Good wall apposition
- Perfusion of the parent artery
- Retention of contrast agent within the aneurysm.

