4.4.3 Rationale for Evaluation Endpoints Selection

Rationale for safety endpoint selection: The safety indicators set for this study aligns with the NMPA requirements, which state, "The observation indicators include at least the following: , related stroke events, and clinical follow-up of deaths, strokes, and disease-related symptoms within 6 months". The recommendation of *Chinese guidelines for the treatment of intracranial aneurysms with flow divertor* is that the vast majority of occlusion of aneurysms after FD implantation occurs within 12 months after treatment. The incidence and severity of AEs/SAEs meet the relevant requirements for safety indicators in the *Guidelines for Clinical Study Design of Medical Devices*.

Rationale for efficacy endpoints selection: This clinical study is conducted in accordance with NMPA requirements to evaluate the long-term follow-up safety information of FRED following its market release. The efficacy indicators set for this study aligns with the NMPA requirements, which state, "The observation indicators include at least the following: technical success rate, re- sheathing performance, perioperative period". In addition, the observational device FRED features a finer mesh design compared to conventional intracranial stents, which allows it to cover the aneurysm neck, redirect blood flow, and promote blood stasis within the aneurysm, leading to thrombus formation and an increased aneurysm occlusion rate. To evaluate the efficacy of the observational device, the clinical study selected the aneurysm occlusion rate as the efficacy endpoint.

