** Each patient may have multiple follow-up information, all of which should be recorded and collected. The collected follow-up data will be divided according to the following follow-up points: 30 days after surgery, 3 months after surgery, 6 months after surgery, and 1 year after surgery, according to the principle of closest approach.

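### Stroke, mortality and adequate-occlusion rates are defined over all patients with no time horizon, so they mix unequal follow-up and are not risks at any stated time point

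*Protocol*

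**What the plan says.** Section 4.4.1 defines the stroke rate: "The stroke rate refers to the proportion of stroke patients in the total number of patients". It defines mortality likewise: "Mortality refers to the proportion of dead patients in the total number of patients". Section 4.4.2 defines the occlusion rate as the "proportion of patients judged to be Grade 1 or Grade 2 in the total number of patients". None of the three carries a time point, a minimum follow-up or a requirement that status be known.

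Elsewhere the protocol does think in time points:

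- Section 4.4.3 cites the regulator's requirement of "clinical follow-up of deaths, strokes, and disease-related symptoms within 6 months", and places most occlusion within 12 months of treatment.
- The note to the follow-up column of Table 4-3 (section 4.5) sorts follow-up data to "30 days after surgery, 3 months after surgery, 6 months after surgery, and 1 year after surgery", by nearest node. That column lists stroke, mortality and Raymond-Roy grade.
- For OKM grade, section 4.4.2 says: "The evaluation results of different follow-up nodes were counted". The mRS definition also refers to different follow-up times.

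Section 5.3.4 gives binary endpoints counts, percentages and exact binomial 95% intervals. It gives survival endpoints Kaplan-Meier estimates, but no endpoint is called a survival endpoint.

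On follow-up length, section 4.1 takes patients who "have received at least one implantation of the observational device between May 2023 and May 2027". Sections 4.2.1 and 5.2 ask for no minimum follow-up. Section 5.4 sets three reporting periods, the last ending in May 2027. Section 4.1.2 gives a duration of about 36 months without a start date.

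**The concern.** A proportion of all patients is a risk only if everyone has been observed for the same time, or if the horizon is so short that all have passed it. Here a patient implanted in May 2023 could contribute four years by May 2027, and one implanted in May 2027 almost nothing. Section 5.5 leaves missing safety data unfilled, so a patient with no later record stays in the denominator and counts as event-free.

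The stated objective is long-term safety and efficacy, reported yearly to the regulator. A rate defined this way can change from one report to the next while the true risk stays the same. The exact binomial interval would not show it, because that interval reflects sampling error and not the mix of follow-up times. Nor could the figure be set against the 6-month horizon in 4.4.3 or the nodes in 4.5.

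**Working it through.** The protocol states no sample size, expected rate or precision, so there is no figure of its own to reproduce. What follows is an illustration.

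**From the protocol.** Counting calendar months inclusively, the stage ends fall T = 25, 37 and 49 months after the start of accrual (sections 4.1 and 5.4).

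**Assumed, not in the protocol.** Uniform implantation; complete follow-up to the cut; cut at the stage end; true 1-year stroke risk 6%. The hazard is either constant or front-loaded, with a share s = 50% or 75% of the 1-year risk in month 1 and the rest accruing evenly over months 1 to 12 and continuing at that pace.

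**Share of patients with short follow-up, h/T.** Under 6 months: 6/25 = 24% at the first cut, 6/49 = 12% at the last. Under 12 months: 12/25 = 48% and 12/49 = 24%.

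**Expected crude rate m(T)**, the average of the cumulative risk F(t) over t uniform on (0, T):

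- Constant hazard: λ = -ln(0.94)/12 = 0.005156 per month; m(T) = 1 - (1 - e^(-λT))/(λT). For T = 49, λT = 0.2527 and m = 11.63%.
- Front-loaded: m(T) = (0.06/T)[s(T - 0.5) + (1 - s)(T - 1)²/22]. For T = 49 and s = 0.75: (0.06/49)(36.375 + 26.182) = 7.66%.

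| Crude stroke rate, true 1-year risk 6% | Constant | 50% in month 1 | 75% in month 1 |
|---|---|---|---|
| Cumulative, all events to date, T = 25 | 6.18% | 6.08% | 5.98% |
| Cumulative, T = 37 | 8.96% | 7.74% | 6.83% |
| Cumulative, T = 49 | 11.63% | 9.38% | 7.66% |
| Split by event date, stage 2 | 4.79% | 3.63% | 2.79% |
| Split by event date, stage 3 | 4.87% | 3.54% | 2.50% |
| Split by implant date, 12-month stage | 3.03% | 4.25% | 5.00% |

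The event-date rows divide the events of the period by all patients implanted so far: (37·m(37) - 25·m(25))/37 and (49·m(49) - 37·m(37))/49. Stage 1 is the T = 25 row under every reading. The true 6-month risk is 3.05%, 4.36% and 5.18% under the three hazards.

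The first-stage value sits near 6% only because follow-up there averages about 12 months (25/2 = 12.5).

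**Sensitivity.** With 90% of the risk in month 1, the formula gives cumulative values of 5.92%, 6.28% and 6.63%, and the implant-date ratio of stage 1 to stage 2 falls to 5.92/5.45 = 1.09. If only events up to 12 months are counted, the cumulative rates are 4.57-5.52% at the first cut and 5.27-5.76% at the last, which is 8-24% and 4-12% below 6% in relative terms. If collection ran 8 months past the last implant (36 months counted from January 2025, an assumption), 4/49 = 8% of patients would be short of 12 months and that shortfall would be only 0.4-1.3%.

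**Fixed-horizon comparison.** In simulation (1,500 runs, 400 patients), the Kaplan-Meier estimate at 12 months is 6.0-6.1% for accrual windows of 12, 25 and 49 months under all three hazards.

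**Occlusion.** Assume adequate occlusion rises linearly to 75% at 12 months, stays there, and everyone is imaged at the cut. The crude proportion is 0.75(T - 6)/T: 57.0%, 62.8% and 65.8% at the three cumulative cuts. Imputation under section 5.5 could change these figures.

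**The case against.** The strongest reply is that the time structure already exists. Section 4.5 allocates follow-up to four nodes, stroke and death dates are recorded, the interval from surgery to occlusion is collected, and Kaplan-Meier allowing for censoring is planned. The definitions in 4.4 could then be read as generic descriptions of a proportion, to be tabulated by node, with the rest left to the analysis plan. Part of this stands: the pieces are there, which is why the repair is cheap. But 4.4 does not merely leave the denominator open; it fixes it as all patients. Node-based or at-risk denominators would depart from that wording.

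Three stronger readings are tempting, and the protocol does not support them.

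- A reader might infer that the protocol ignores patients whose images stop being collected: "If the Raymond-Roy grade reaches Grade I at any evaluation point, no further imaging information will be collected". Section 5.5 names last-value carry-over, mean filling and multiple imputation for missing efficacy endpoints and leaves the rules to the analysis plan. The choice is deferred, not forgotten.
- A reader might lead with the halving between stages (6.18% against 3.03%). That needs stages split by implant date. Section 5.4 speaks of dividing collected data by collection period, which leans the other way without being conclusive.
- A reader might infer a bias of known direction. Long follow-up pushes the crude stroke and death proportions up, and short or absent follow-up pushes them down. The net effect depends on the cut-off and on event timing.

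It is also fair that Kaplan-Meier is not free of problems in chart review, because a last contact may itself be triggered by an event.

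**Conclusion.** The point holds and should be fixed. As written, the three rates are crude proportions over unequal follow-up. They are neither the 6-month risk cited in 4.4.3 nor a risk at any node in 4.5, and they can move between stage reports with unchanged true risk.

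Under the stated assumptions, the cumulative crude stroke rate drifts from 6.0-6.2% to 6.8-9.0% and then 7.7-11.6%. Split by event date, it goes from 6.0-6.2% to 2.8-4.8% and 2.5-4.9%. Accrual pattern, the 6% risk, hazard shape and cut dates are all assumed, and the drift becomes small if nearly all events occur in the first month. The study is descriptive, so no test, decision rule or success criterion is affected.

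**What to change.** - **Sections 4.4.1 and 5.3.4.** Name all-cause mortality and stroke as the endpoints for the Kaplan-Meier method already planned; treating death as a competing event for stroke is an option. Report both at 30 days, 6 months and 1 year from the first FRED procedure, censored at last documented contact, with numbers at risk.
- **Section 4.4.2.** Report adequate occlusion at each node of section 4.5 among patients implanted long enough before the data cut to be due. Show the number not imaged. Align the handling of patients whose image collection stopped at Grade I with the imputation rule of section 5.5, for example by carrying Grade I forward.
- **Section 5.4.** Keep the three periods and show the 1-year estimates in a cumulative summary. As clarification, state whether periods are split by implant or collection date, and the follow-up cut-off for the last implants.

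**Cost.** Mostly wording. Stroke and death dates and the nodes already exist. A last-contact date is not among the listed items, so one eCRF field may be needed. Intervals are wider at early cuts: in a 12-month stage split by implant date and cut at its end, the simulated SD of the 1-year estimate is 1.7-2.9 percentage points against 0.9-1.1 for the crude rate (400 patients assumed), while the 6-month estimate stays usable at 1.0-1.2. The possibility that last contact is triggered by events should be stated as a limitation.

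### The lesion-related complication rate in 4.4.1(4) mixes puncture-site events with target-vessel and aneurysm events, so as written it overstates harm at the lesion

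*Protocol*

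**What the plan says.** Protocol section 4.4.1(4) gives this definition: "Lesion-related complication refers to the proportion of patients with lesion-related complication to total patients". It does not say what makes a complication lesion-related. The text under its collection heading supplies the only concrete content:

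- It begins with "Complications of arterial puncture: including puncture site pain, puncture site local bleeding", and adds damage to the punctured artery or to nearby nerves.
- It continues with parent-artery dissection or perforation, "Rupture or perforation of the aneurysm", vasospasm and stent thrombosis.
- It ends with "Other complication", with no limit on site or cause.

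The Principal Investigator "shall evaluate the relationship between complications and observational device, other interventional devices, and surgical procedures".

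Section 4.3.3 collects the same named items under a different label: "Procedure complication: Complications of arterial puncture including pain, local bleeding, or injury to the artery, or adjacent nerves", followed by the same vessel, aneurysm, vasospasm and stent items.

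Section 4.4.1(3), the lesion-related symptoms or signs rate, limits collection to neurological symptoms that are new or worse than at baseline. Its list nevertheless contains "bleeding (including intracerebral, subarachnoid hemorrhage, retroperitoneal, others".

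Under section 5.3.4, binary endpoints are reported as counts and percentages with exact binomial 95% intervals. Under section 11, only CEC determinations enter the safety endpoint analysis.

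**The concern.** The device is indicated for the internal carotid artery from the petrous segment to the terminus (sections 2.3.1 and 2.3.2), while the puncture is femoral or radial (section 4.3.3). Pain or bleeding at the puncture site is therefore not an event at the treated lesion. If it counts in endpoint (4), a patient with puncture-site pain and a patient with aneurysm rupture contribute equally to a figure labelled lesion-related.

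The study is descriptive, so the published percentage and its interval are the whole result, and they feed the yearly analyses in section 5.4. A reader would take the figure as the frequency of harm at the aneurysm or parent artery. Because the data come retrospectively from charts, the figure would also move with how carefully each site records puncture-site pain.

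In endpoint (3), retroperitoneal bleeding is neither neurological nor at the lesion, so the list conflicts with its own entry condition.

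**Working it through.** The plan states no event rate, threshold or sample size for these endpoints, so there is no figure of its own to reproduce. The check has two parts.

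**1. Does any stated rule keep non-lesion events out of endpoint (4)?**

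- *Definition, 4.4.1(4):* circular, with no criterion.
- *Investigator, 4.4.1(4):* attributes each complication to the device, other devices or the surgical procedure. There is no category for the lesion or the access site.
- *CEC, 10.1.3:* judges severity and relevance to devices or procedures, not to the lesion.
- *CEC, section 11:* adjudicates events associated with the device or the procedure. A puncture-site bleed is associated with the procedure, so it passes.
- *Section 4.3.3:* gives the same named items as procedure complications, which is the more accurate label.

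No stated rule removes the access-site items.

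**2. How far could the reported rate exceed the lesion rate?**

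Let L be the proportion of patients with a target-vessel or aneurysm complication and A the proportion with an access-site complication. Both are assumptions, and the two are taken as independent.

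- Reported rate: R = 1 − (1 − L)(1 − A)
- Excess over the lesion rate: R − L = A(1 − L)
- Share of counted patients with an access-site event only: (R − L)/R

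With L = 5%:

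| A | R | Excess (percentage points) | Access-only share |
|---|---|---|---|
| 1% | 1 − 0.95 × 0.99 = 6.0% | 0.95 | 16% |
| 3% | 1 − 0.95 × 0.97 = 7.9% | 2.85 | 36% |
| 5% | 1 − 0.95 × 0.95 = 9.8% | 4.75 | 49% |
| 10% | 1 − 0.95 × 0.90 = 14.5% | 9.5 | 66% |

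For other values of L, at the same four values of A:

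- L = 2%: R = 3.0%, 4.9%, 6.9%, 11.8%; access-only share 33%, 60%, 71%, 83%.
- L = 10%: R = 10.9%, 12.7%, 14.5%, 19.0%; access-only share 8%, 21%, 31%, 47%.

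Access-only patients form the majority when A(1 − L) > L, that is A > L/(1 − L). For L = 5% the threshold is 0.05/0.95 = 5.3%. The open item for other complications could add more, but nothing in the protocol allows that to be sized.

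**Endpoint (3).** Assume retroperitoneal bleeding in 0.2% to 1% of patients and the other listed symptoms in 5% to 20%. The same formula gives a retroperitoneal-only share of 0.8% (0.2% with 20%) to 16% (1% with 5%). The defect there is mainly one of definition.

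**The case against.** The strongest reply is that the list stands under a collection heading, while the definition line still says lesion-related. The CEC could therefore filter events, under bylaws or a charter (sections 4.6 and 8.3) that are not at hand. That is possible, and it means that counting puncture-site pain is an inference from the text. But the protocol gives neither the CEC nor the investigator a lesion criterion, and the only relatedness targets it names would let access-site events through.

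A second reply is that little depends on it: there is no hypothesis test, section 5.6 sets no success criterion, the components are listed separately, and a breakdown by component could be left to the analysis plan. This rightly limits the severity. It does not cure a label and a component list that disagree in the protocol itself.

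A reader might also infer more than the document supports:

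- *That the two rates do not measure lesion harm at all.* Both lists contain genuine lesion or target-vessel events, such as aneurysm rupture, parent-artery perforation, subarachnoid hemorrhage and oculomotor palsy. The rates are mixed.
- *That access-site events dominate both rates.* Puncture-site pain appears only in endpoint (4). Even there, domination depends on rates the document does not give, and at 5% and 5% the access-only share is 49%. For endpoint (3) domination is not supported.
- *That listing stroke in endpoint (3) as well as in endpoint (1) is an error.* Stroke is neurological and can be lesion-related. The endpoints are reported separately, and nothing adds them together.

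**Conclusion.** The point holds as a mismatch between label and content, and it is minor. As written, endpoint (4) is a procedure-complication rate reported under a lesion-related name, and it overstates lesion-related harm by A(1 − L). With L = 5% that is about 1 to 9.5 percentage points for access-site rates of 1% to 10%. The size rests on assumed rates, on independence, and on the listed events being counted without a further filter. The direction needs only that some patients have a puncture-site event and no lesion event. In endpoint (3), retroperitoneal bleeding contradicts the restriction to neurological symptoms, with a likely small numerical effect.

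**What to change.** In section 4.4.1(4), and in the synopsis to match:

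- Report the full list as a procedure-complication rate, in line with the label in 4.3.3.
- Compute the lesion-related rate only from parent-artery dissection or perforation, aneurysm rupture or perforation, vasospasm, stent thrombosis and other *intracranial* complications.
- Report access-site complications as a separate rate.

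In section 4.4.1(3), remove retroperitoneal (non-neurological) bleeding from the numerator and report it as an AE or SAE at any time. It should not simply be moved into endpoint (4): that endpoint records complications during the procedure, and the synopsis marks it as immediate post-procedure, so a later bleed could be lost.

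The cost is a change of wording and one or two extra table rows. No new data are needed, because the components are already listed as separate items. The lesion-related rate will rest on fewer events.
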